8.3.1.1 INFUSION RELATED REACTIONS AND INFUSION RATE GUIDANCE – UBLITUXIMAB

Infusion related reactions including severe reactions have been reported with ublituximab administration in subjects with CLL. Guidelines are provided below for subjects who experience such reactions. Symptomatic infusion reactions, despite premedication, may be treated at the discretion of the treating physician, including but not limited to: oral acetaminophen 650 mg (or equivalent), corticosteroids, antihistamines, oxygen, and bronchodilators.

The following are recommended infusion rate reduction/delay guidelines for subjects who experience severe Infusion Related Reactions (IRR's) in which treatment should be interrupted. Final decision for infusion rate reduction/delay or discontinuation resides with the treating investigator.

1st or 2nd Infusion Interruption:

- Hold infusion and closely monitor subject, institute symptomatic medical management until resolution of IRR symptoms.

- Following the judgment of the Investigator, and provided the subject is stable, the infusion may be resumed at no more than half the previous rate.
- If the subject does not experience any further IRR symptoms, infusion rate escalation may resume at the increments and intervals as appropriate at the treatment cycle dose (see Section 8.3.1.2).

3rd Infusion Interruption (same day):

- Discontinue infusion for that day – monitor subject for resolution of all symptoms. Subject should have all vital signs completed as well as any other standard of care procedures completed as warranted by the Investigator prior to release of subject from study site.
- Any remaining diluted investigational product should be discarded.

If the infusion discontinued is the Cycle 1 Day 1 infusion, administer the scheduled Cycle 1 Day 2 dose according to the protocol dosing schedule. During retreatment, if the infusion discontinued is the Cycle 3 Day 1 infusion, administer the scheduled Cycle 3 Day 2 dose according to the protocol dosing schedule.

If at any time during ublituximab treatment, an infusion related reaction is observed, the treating investigator may reduce the infusion flow rate at their discretion.

8.3.1.2 FLOW RATE RECOMMENDATIONS FOR UBLITUXIMAB ADMINISTRATION

Cycle 1 Day 1 & 2 infusion over 4 hours (Retreatment Cycle 3 Day 1 & Day 2)

Cycle 1	Ublituximab Dose	Total volume to be infused	Infusion rate			
			T0 to T30'	T30' to T1H	T1H to T2H	T2H to T4H
Day 1	150 mg	250 mL	10 mL/H	20 mL/H	35 mL/H	100 mL/H
Day 2	750 mg	500 mL	10 mL/H	20 mL/H	85 mL/H	200 mL/H

Cycle 1 Day 8 & 15 infusions over 3 hours (Retreatment Cycle 3 Days 8 & Day 15)

Ublituximab Dose	Total volume to be infused	Infusion rate		
		T0 to T1H	T1H to T2H	T2H to T3H
900 mg	500 mL	50 mL/H	150 mL/H	300 mL/H

Cycle 2 and remaining infusions over 90 minutes (Retreatment Cycle 4 and beyond)

Ublituximab Dose	Total volume to be infused	Infusion rate	
		T0 to T30min	T30min to T90min
900 mg	500 mL	200 mL/H	400 mL/H

8.3.1.3 DISPENSING OF UBLITUXIMAB

Before dispensing, the site pharmacist or authorized study site representative must check that the ublituximab is in accordance with the product specifications and the validity is within the re-test date.

The exact dose and the date and time of administration of ublituximab must be recorded within the eCRF, subject's medical records, and/or in the drug accountability records. The Pharmacist or authorized study site representative should record the date dispensed and subject's number and initials, as well as complete the accountability record in the electronic drug accountability system with information concerning the dispensation of ublituximab. Preparation should be done by the Pharmacist or authorized study site representative according to instructions for sterile dilution.

8.3.1.3.1 DILUTIONS OF UBLITUXIMAB

Ublituximab should not be mixed with other medicinal products. Ublituximab should only be diluted in 0.9% NaCl before use.

Ublituximab vials containing 6 mL (25 mg/mL)

Dilutions for Cycle 1 Day 1 & Day 2 (Retreatment Cycle 3 Day 1 & Day 2)

Dose of ublituximab for infusion	
Cycle 1 Day 1: 150 mg	
Cycle 1 Day 2: 750 mg	

Dilutions for \geq Cycle 1 Day 8 Infusions (Retreatment \geq Cycle 3 Day 8)

Dose of ublituximab for infusion	
900 mg	

8.3.2 GUIDELINES FOR ADMINISTRATION OF UMBRALISIB

- *Method of Administration:* Umbralisib will be administered orally once daily at approximately the same time with food
- *Potential Drug Interactions:* No Drug Interactions have been reported to date.
- *Pre-medications:* Subjects are required to start prophylaxis for pneumocystis jiroveci pneumonia (PJP) and antiviral therapy prior to Cycle 1 Day 1 of initial treatment and prior to Cycle 3 Day 1 during retreatment. The following prophylaxis approaches are recommended:
 - *Anti-viral Prophylaxis:* Valtrex 500 mg daily or Acyclovir 400 mg BID or equivalent.
 - *PJP Prophylaxis:* Dapsone 100 mg daily or Atovaquone 1,500 mg once daily or equivalent

Final choice of PJP and anti-viral prophylaxis therapy and schedule is per investigator discretion.

If anti-viral or anti-bacterial prophylaxis is not tolerated, we recommend alternating to a different prophylactic agent, reducing the dose or modifying the schedule for the prophylactic agent, or discontinuing prophylaxis at investigator discretion.

Umbralisib will be dispensed at the sites by the research coordinator or designee under the direction of the PI or by a pharmacist at the site. Subjects must be provided drug in its original container. Subjects should be instructed to return all empty and partially filled bottles with any unused tablets when they return to the site. For the purpose of drug accountability and dosing, subjects should record any missed doses of umbralisib on a drug diary. Study drug compliance should be reviewed with the subject at the beginning of each new treatment cycle and as needed. Missed doses will be documented in the subjects' medical record.

Umbralisib will be self-administered by the subject. Tablets should be taken at approximately the same time each day with food. Subjects should be instructed to swallow the tablets whole and should not chew or crush them.

If a dose of umbralisib is missed, it should be taken as soon as possible on the same day. If it is missed for a period greater than 12 hours, it should not be replaced. If vomiting occurs, no attempt should be made to replace the vomited dose.

8.3.2.1 DISPENSING OF UMBRALISIB

Before dispensing, the site pharmacist or his/her representative must check that the umbralisib is in accordance with the product specifications and the validity is within the re-test date.

The exact dose and the date of administration of umbralisib must be recorded within the eCRF, subject's medical records, and/or in the drug accountability records. Any error in drug administration (e.g., missed dose) should be recorded in the eCRF. The pharmacist or his/her representative should record the date dispensed and subject's number and initials, as well as complete the accountability record in the electronic drug accountability system with information concerning the dispensation of umbralisib.

8.3.3 GUIDELINES FOR ADMINISTRATION OF IBRUTINIB

- *Method of Administration:* Ibrutinib will be administered orally once daily with water.
- *Potential Drug Interactions:* Avoid co-administration with moderate or strong CYP3A inhibitors and/or inducers. If a moderate or strong CYP3A inhibitor must be used, follow the prescribing information. Also avoid grapefruit and Seville oranges during treatment, as these contain moderate inhibitors of CYP3A and can alter ibrutinib pharmacokinetics.

- *Pre-medications:* None

Ibrutinib will be self-administered by the subject. Tablets should be taken at approximately the same time each day. Subjects should be instructed to follow all package insert instructions. This includes instruction that tablets are to be swallowed whole, not chewed or crushed. If a dose is missed for the entire day, it should not be replaced. If vomiting occurs, no attempt should be made to replace the vomited dose.

Study drug compliance should be reviewed with the subject at the beginning of each new treatment cycle. Missed doses should be documented in the subject drug diary. No routine prophylactic antiemetics or premedications should be given outside of protocol requirements. However, these medications may be administered for symptoms when they occur and may be given prophylactically afterward. Refer to the ibrutinib package insert for full details at www.imbruvica.com

8.3.4 GUIDELINES FOR ADMINISTRATION OF ACALABRUTINIB

- *Method of Administration:* Acalabrutinib will be administered orally every 12 hours; swallow whole with water and with or without food.
- *Potential Drug Interactions:* CYP3A Inhibitors – Avoid co-administration with strong CYP3A inhibitors. Dose adjustments may be recommended. CYP3A Inducers – Avoid co-administration with strong CYP3A inducers. Dose adjustments may be recommended. Gastric Acid Reducing Agents – Avoid co-administration with proton pump inhibitors (PPIs). Stagger dosing with H2-receptor antagonists and antacids.
- *Pre-medications:* None

Acalabrutinib will be self-administered by the subject. Tablets should be taken every 12 hours. Subjects should be instructed to follow all package insert instructions. This includes instruction that tablets are to be swallowed whole, not chewed or crushed. If a dose is missed for more than 3 hours, it should not be replaced.

Study drug compliance should be reviewed with the subject at the beginning of each new treatment cycle. Missed doses should be documented in the subject drug diary. No routine prophylactic antiemetics or premedications should be given outside of protocol requirements. However, these medications may be administered for symptoms when they occur and may be given prophylactically afterward. Refer to the acalabrutinib package insert for full details at <https://www.azpicentral.com/calquence/calquence.pdf#page=1>.

8.3.5 GUIDELINES OF ADMINISTRATION FOR VENETOCLAX

- *Method of Administration:* Venetoclax will be administered orally once daily with food or water

- **Potential Drug Interactions:** Avoid co-administration with moderate or strong CYP3A inhibitors. If a moderate or strong CYP3A inhibitor must be used, follow the prescribing information. Also avoid grapefruit and Seville oranges during treatment, as these contain moderate inhibitors of CYP3A and can alter venetoclax pharmacokinetics.
- **Pre-medications:** None

[REDACTED] Venetoclax will be self-administered by the subject. Tablets should be taken at approximately the same time each day with food or water. Subjects should be instructed to swallow the tablets and should not chew or crush them. If a dose of venetoclax is missed, it should be taken as soon as possible on the same day. If it is missed greater than 8 hours from scheduled dosing, it should not be replaced. If vomiting occurs, no attempt should be made to replace the vomited dose.

Study drug compliance should be reviewed with the subject at the beginning of each new treatment cycle. Missed doses should be documented in the subject drug diary.

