9.5.3 PHARMACODYNAMICS AND PHARMACOKINETICS

Absorption

Following multiple oral administrations under fed conditions, maximum plasma concentration of venetoclax was reached 5-8 hours after dose. Venetoclax steady state AUC increased proportionally over the dose range of 150-800 mg. Under low-fat meal conditions, venetoclax mean (\pm standard deviation) steady state C_{max} was $2.1 \pm 1.1 \mu\text{g}/\text{mL}$ and AUC_{0-24} was $32.8 \pm 16.9 \mu\text{g}\cdot\text{h}/\text{mL}$ at the 400 mg once daily dose.

Food Effect

Administration with a low-fat meal increased venetoclax exposure by approximately 3.4-fold and administration with a high-fat meal increased venetoclax exposure by 5.1-to 5.3-fold compared with fasting conditions. Venetoclax should be administered with a meal.

Distribution

Venetoclax is highly bound to human plasma protein with unbound fraction in plasma <0.01 across a concentration range of 1-30 μM (0.87-26 $\mu\text{g}/\text{mL}$). The mean blood-to-plasma ratio was 0.57. The population estimate for apparent volume of distribution (V_{dss}/F) of venetoclax ranged from 256-321 L in subjects.

Elimination

The population estimate for the terminal elimination half-life of venetoclax was approximately 26 hours. The pharmacokinetics of venetoclax does not change over time.

Metabolism

In vitro studies demonstrated that venetoclax is predominantly metabolized by CYP3A4/5. M27 was identified as a major metabolite in plasma with an inhibitory activity against BCL-2 that is at least 58-fold lower than venetoclax *in vitro*.

Excretion

After single oral administration of 200 mg radiolabeled [¹⁴C]-venetoclax dose to healthy subjects, >99.9% of the dose was recovered in feces and <0.1% of the dose was excreted in urine within 9 days, indicating that hepatic elimination is responsible for the clearance of venetoclax from the systemic circulation. Unchanged venetoclax accounted for 20.8% of the administered radioactive dose excreted in feces.

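### Section 8.3.5 lets venetoclax be taken with water alone, while Section 9.5.3 calls for a meal and reports 3.4- to 5.3-fold higher exposure with food than fasting

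*Combined protocol and SAP*

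**What the plan says.** Section 8.3.5, which tells sites how venetoclax is given, states the rule twice. The method bullet reads "Venetoclax will be administered orally once daily with food or water". The self-administration paragraph reads "Tablets should be taken at approximately the same time each day with food or water". Both sentences are complete; the redaction in that section falls just before the self-administration text and does not cut into either.

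Section 9.5.3, under its food-effect paragraph, says "Venetoclax should be administered with a meal". The reason is given there: relative to fasting, exposure rises about 3.4-fold after a low-fat meal, and for the richer meal the text reads "administration with a high-fat meal increased venetoclax exposure by 5.1-to 5.3-fold compared with fasting conditions".

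The neighbouring sections set out food rules for other oral drugs. Umbralisib (Section 8.3.2): "Umbralisib will be administered orally once daily at approximately the same time with food". Acalabrutinib (Section 8.3.4): "swallow whole with water and with or without food". For acalabrutinib the protocol adds "Subjects should be instructed to follow all package insert instructions", and Section 8.3.3 has the same instruction for ibrutinib. The visible text of Section 8.3.5 has no such instruction.

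**The concern.** The two sections cannot both be the intended rule. Because 8.3.5 joins food and water with *or*, a subject who takes the tablets on an empty stomach with a glass of water has followed it. Section 9.5.3 does not allow that. Section 8.3.5 is also the place a site would look when instructing a subject, so the looser wording sits in the operative text and the correct wording in the background.

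The protocol otherwise takes care over influences on venetoclax levels. Exclusion criterion 8 bars strong and moderate CYP3A inhibitors and inducers, and 8.3.5 itself tells subjects to avoid grapefruit and Seville oranges for pharmacokinetic reasons. Leaving the meal optional does not fit with that.

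What is at stake is control of delivered exposure in Cohort B. A fasted and a fed dose look identical in the summaries planned in Section 11.5, which cover milligrams, number of doses and cycles. The assessment schedules in Section 7 list no venetoclax concentration sampling. Food status is not a usual part of an exposure summary, so this is no fault in 11.5; it only means that the variation would go unseen.

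**Working it through.** The plan gives no statistical figure to reproduce on this point. The check is a comparison of text, followed by arithmetic on the food-effect ratios.

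**Text side by side**

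| Section | Drug | Rule on food | Does water alone comply? |
|---|---|---|---|
| 8.3.5 (twice) | Venetoclax | Food or water | Yes |
| 9.5.3 | Venetoclax | A meal | No |
| 8.3.2 | Umbralisib | Food | No |
| 8.3.4 | Acalabrutinib | Water, food optional | Yes, and said expressly |

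Section 8.3.4 treats water and food as two separate matters. Section 8.3.5 runs them together as alternatives.

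**Does other visible text settle the daily rule?** The places that refer to the venetoclax label or prescribing information were checked:

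- 8.3: inpatient or outpatient setting
- 8.3.5: use of a CYP3A inhibitor
- 8.3.5.1: dose escalation and tumour lysis prophylaxis in re-treatment
- 8.4.3: toxicity and dose modification
- 9.5.1: safety information

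None visibly governs food with the daily dose outside the ramp-up.

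**Inputs for the size, all from Section 9.5.3**

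- Low-fat meal relative to fasting: 3.4
- High-fat meal relative to fasting: 5.1 to 5.3
- Mean steady-state AUC0-24 at 400 mg once daily under low-fat-meal conditions: 32.8 µg·h/mL

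**Fasting exposure as a share of fed exposure** (reciprocal of the ratio)

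- Against a low-fat meal: 1/3.4 = 0.294, or 29.4%
- Against a high-fat meal: 1/5.1 = 0.196 and 1/5.3 = 0.189, or 18.9% to 19.6%

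**Spread in exposure at one milligram dose**

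- Under 8.3.5 (fasting up to a high-fat meal): 5.1- to 5.3-fold
- With a meal required (low-fat up to high-fat): 5.1/3.4 = 1.50 to 5.3/3.4 = 1.56, so about 1.50- to 1.56-fold

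**Illustration on the AUC scale**

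- Implied fasting AUC0-24 at 400 mg: 32.8/3.4 = 9.6 µg·h/mL

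This last figure assumes that the 3.4 ratio applies to AUC, since 9.5.3 speaks only of exposure, and that it holds at steady state. The conflict between the sections does not depend on it.

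**The case against.** The strongest reply is that this is a slip of one word with little practical reach. The correct rule already stands in the same protocol. Cohort B subjects have taken venetoclax for at least 6 months before entry and continue at a dose they tolerate, so they bring established habits. Escalation in re-treatment, where tumour lysis is the worry, follows the label under 8.3.5.1. During triplet therapy every Cohort B subject is also assigned daily umbralisib with food, so a daily dose with food is already part of the regimen. The percentages are a worst case, because taking tablets with water does not mean the subject has fasted. Finally, the redaction in 8.3.5 could hide a pointer to the package insert.

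Much of this stands as mitigation. It lowers the likely frequency of fasted dosing, and it confines the conflict to daily intake outside the ramp-up. It does not reconcile the two sections:

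- No visible text requires venetoclax and umbralisib to be taken together. The first two re-treatment cycles are venetoclax alone, including Cycle 2 Days 8 to 28, after the scheduled escalation window. Section 8.4.2 lets a subject who stops one study drug continue the others.
- If the *or* is a slip for *and*, it was made twice, and correcting it is exactly the remedy.
- The redaction limits how much weight the missing package-insert instruction can bear, but not the plain meaning of the two complete sentences.

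**Conclusion.** The concern holds: the dosing instruction in 8.3.5 is wrong as written and contradicts 9.5.3. This is an internal inconsistency in an operative section, not a flaw in the statistical design. By the protocol's own ratios, a subject can comply with 8.3.5 and receive between about a fifth and under a third of the fed exposure at the same dose. Those shares apply to a dose that is actually taken fasting; 8.3.5 permits this but does not require it.

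How often it would happen is unknown from the documents, and they contain no exposure-response relation for MRD. Nothing is therefore claimed about bias in the Cohort B U-MRD rate, and no planned analysis changes. The correction should be made because the possible spread in exposure is large, would not be visible in the planned summaries, and costs almost nothing to remove.

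**What to change.** In Section 8.3.5, reword both the method bullet and the self-administration sentence so that venetoclax is taken with a meal and water, in line with 9.5.3. Check that any subject dosing instructions and the drug diary say the same; that text is not among the documents and may already be correct.

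The cost is a change to two sentences in one section, plus a check of the subject materials. No visit, assessment, sample size or analysis is affected.

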8.3.5.1 DOSE ESCALATION OF VENETOCLAX (RETREATMENT PHASE)

All dose escalation of venetoclax and tumor lysis syndrome prophylaxis should be executed per FDA approved label and package insert refer to <https://www.venclextahcp.com> . Study drug compliance should be reviewed with the subject at the beginning of each new treatment cycle and as needed. Missed doses will be documented in the subjects' medical record and drug diary.

Venetoclax starting pack provides the first 4 weeks according to the ramp-up schedule. Once the ramp-up phase is completed, the 400 mg dose is achieved using 100 mg tablets supplied in bottles.

Tumor lysis risk, Prophylaxis and Assessments

Tumor Burden		Prophylaxis		Blood Chemistry ^b
		Hydration	Anti-hyperuricemics	Assessments
Low	All LN <5cm AND ALC<25 x10 ⁹ /L	Oral (1.5-2L daily)	Allopurinol ^a	
Outpatient
 
 • For first dose of 20 mg and 50 mg: Pre-dose, 6 to 8 hours, 24 hrs • Pre-dose at subsequent ramp-up doses

Medium	Any LN 5cm to <10cm OR ALC \geq 25 x10 ⁹ /L	Oral (1.5-2L daily), And consider additional Intravenous	Allopurinol ^a	Outpatient 
 For first dose of 20 and 50mg: Pre-dose, 6 to 8 hours, 24 hours For subsequent ramp up doses: Pre-dose For first dose of 20mg and 50mg: Consider hospitalization with CrCl <80ml/min
High	Any LN \geq 10cm OR ALC \geq 25 x10 ⁹ /L AND Any LN \geq 5cm	Oral (1.5-2L daily), and intravenous (150-200 mL/IV as tolerated)	Allopurinol ^a , consider rasburicase if baseline uric acid is elevated	Inpatient at first dose of 20 and 50mg 
 Pre-dose, 4, 8, 12, and 24 hours Outpatient for subsequent ramp-up doses 
 Pre-dose, 6 to 8 hours, 24 hours

ALC = absolute lymphocyte count; LN = lymph node; hrs = hours

^aStart allopurinol or alternate xanthine oxidase inhibitor 2-3 days prior to venetoclax if not administering rasburicase

^b Blood Chemistries include potassium, calcium, phosphorus, uric acid and creatinine

8.3.6 CRITERIA FOR ONGOING RE-TREATMENT

Continue treatment as per protocol provided the subject has:

- No intolerable toxicities related to study drug.
- D-MRD or has not completed 26 cycles of re-treatment .
- No clinical or radiographic evidence of disease progression.
- Not withdrawn from the study for other reasons.

